PROTOCOL TITLE

Open-Label Prospective Randomized Control Trial to Investigate the Efficacy of Omega-3 Fatty Acid Therapy in Preventing Gastrointestinal Bleeding in Patients with Continuous-Flow Left Ventricular Assist Device

Version: 05Jun2019

NCT03784963

PROTOCOL TITLE

Open-Label Prospective Randomized Control Trial to Investigate the Efficacy of Omega-3 Fatty Acid Therapy in Preventing Gastrointestinal Bleeding in Patients with Continuous-Flow Left Ventricular Assist Device

PRINCIPAL INVESTIGATOR

[name]
Department of Medicine, Section of Cardiology
[contact]

OBJECTIVES

Aim 1: We will evaluate whether high-dose omega-3 fatty acid (O3FA) supplementation alters markers of angiogenesis and inflammation in patients with continuous-flow left ventricular assist devices (CF-LVAD).

- **Aim 1a** will assess the effect of high-dose O3FA in patients who have not experienced an episode of gastrointestinal (GI) bleeding. Patients will be enrolled up to 3 months following CF-LVAD implantation and randomized to high-dose O3FA or none. Markers of angiogenesis and inflammation will be assessed prior to and following initiation of high-dose O3FA therapy.
- **Aim 1b** will assess the effect of high-dose O3FA in CF-LVAD patients who have already experienced a GI bleeding event. Patients who have experienced a prior bleeding event will be enrolled and randomized to high-dose O3FA or none. Markers of angiogenesis and inflammation will be assessed prior to and following initiation of high-dose O3FA therapy.

Aim 2: We will assess the changes that occur to the microbiome of CF-LVAD patients following O3FA supplementation.

Aim 3: We will assess the effect of high-dose O3FA supplementation on GI bleeding events in both the population without prior GI bleeding events, and the population with prior GI bleeding events.

BACKGROUND

Continuous-flow left ventricular assist devices (CF-LVAD) have become the mainstay of therapy for advanced heart failure, both as bridge to transplantation and as destination therapy, allowing significant improvement in survival. However, this therapy is limited by a high adverse event profile, specifically those related to hemocompatibility.

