For O3FA subjects:
-Provide O3FA supplement
-Subjects will be instructed to take 4 pills a day
-Study drug compliance check

3 months post-randomization

Record medical history and medications

Collect stool sample

Collect blood sample

Record adverse events

For 03FA subjects:

- Provide O3FA supplement

- Subjects will be instructed to take 4 pills a day

- Study drug compliance check

4.5 months post-randomization

Record medical history and medications

Record adverse events

For 03FA subjects:

- Provide O3FA supplement

- Subjects will be instructed to take 4 pills a day

- Study drug compliance check

6 months post-randomization

Record medical history and medications

Collect stool sample

Collect blood sample

Record adverse events

For 03FA subjects:

- Provide O3FA supplement

- Subjects will be instructed to take 4 pills a day

- Study drug compliance check

7.5 months post-randomization

Record medical history and medications

Record adverse events

For 03FA subjects:

- Provide O3FA supplement

- Subjects will be instructed to take 4 pills a day

- Study drug compliance check

9 months post-randomization

Record medical history and medications

Record adverse events

For 03FA subjects:

- Provide O3FA supplement

- Subjects will be instructed to take 4 pills a day

- Study drug compliance check

10.5 months post-randomization

Record medical history and medications

Record adverse events

For 03FA subjects:

- Provide O3FA supplement

- Subjects will be instructed to take 4 pills a day

- Study drug compliance check

1 year post-randomization

Record medical history and medications

Collect stool sample

Collect blood sample

Record adverse events

For O3FA subjects:

-No more O3FA supplements will be provided by the study

-Study drug compliance check

Stool Collection for Microbiome Sequencing Analysis

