Complete metabolic panel including liver function tests, complete blood count, lipid profile, and inflammatory markers (hs-CRP and ESR) will be collected as standard of care. Approximately 20mL of peripheral blood will be collected and tested for markers of angiogenesis using a multiplex immunoassay system (Biorad). The angiogenesis factors to be measured are angiopoietin-2, epidermal growth factor (EGF), endoglin, sCD40L, vascular endothelial growth factor A, C and D, (VEGF-A, -C, -D), placental growth factor (PIGF), heparin-binding EGF-like growth factor (HB-EGF), plasminogen activator inhibitor-1 (PAI-1), insulin-like growth factor binding protein (*IGFBP*)-1, transforming growth factor alpha (TGF- α), and urokinase-type plasminogen activator (uPA). The inflammatory markers to be measured are Interleukin-6 (IL-6), Interleukin-8, Interleukin-18 (IL-18), sCD40L, soluble Fas ligand (sFASL), and TNF α .

Data will be collected from the subjects' medical records for up to 2 years post-randomization to collect outcomes and adverse events.

GIB episodes will be defined by INTERMACS:

An episode of SUSPECTED INTERNAL OR EXTERNAL BLEEDING that results in 1 or more of the following:

1. Death
2. Re-operation
3. Hospitalization
4. Transfusion of red blood cells as follows:
 - During first 7 days post implant (≥ 4 units packed red blood cells within any 24-hour period in patients $\geq 50\text{kg}$ or $\geq 20\text{cc/kg}$ packed red blood cells within any 24-hour period in patients $< 50\text{kg}$)
 - After 7 days post implant (transfusion of packed red blood cells (PRBC) after 7 days following implant with the investigator recording the number of units given.)

During the 1-year study period, clinical events including GIB and other major adverse events will be recorded and evaluated on a regular basis.

DATA AND SPECIMEN BANKING

Peripheral blood collected from consented participants will be stored in refrigerators at -80C for the duration of the study. All members of the research team will have access to the specimens.

Stool samples collected from consented participants will be shipped straight to [name] laboratory for microbiome analysis and storage. All samples will receive a designated study code. This code will be linked to the patient's data.

All samples, blood and stool, will be stored indefinitely for future research related to heart failure, GI bleeding, Omega-3 supplements, and microbiome.

STUDY TIMELINES

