Each subject will actively participate in the study for 1 year after randomization. We will collect data from the subjects' medical records for an additional year. It will take approximately 6 months to enroll all study participants. Once the study is complete, it will take approximately 3 months to complete the primary analysis.

INCLUSION AND EXCLUSION CRITERIA

Inclusion Criteria

1. Subject has signed consent
2. Age ≥ 18 years
3. Subjects with a CF-LVAD or are scheduled to receive a CF-LVAD implant

Exclusion Criteria:

1. Psychiatric disorder or disease, irreversible cognitive dysfunction or psychosocial issues that might impair compliance with the study.
2. Patients already taking O3FA.

RECRUITMENT METHODS

Patients with advanced heart failure will be seen in clinic, in the cardiac catheterization laboratory, or inpatient wards or intensive care units. If the patient goes on to have an evaluation for LVAD during their clinical course, a member of the research team will approach the patient. We currently implant approximately 60 CF-LVAD per year at the University of

Chicago. Recruitment from the recently implanted cohort and newly implanted patients should provide us with sufficient patients for this study.

COMPENSATION FOR PARTICIPATION IN RESEARCH ACTIVITIES

There will be no compensation to participants in this study.

WITHDRAWAL OF PARTICIPANTS

Participants can be withdrawn without consent if they are not compliant with taking O3FA daily. They will be notified of withdrawal and all their data will be permanently erased. If participants decide to withdraw from the study, all of the O3FA will be returned to the research team, and the all of their data will be permanently erased.

RISKS TO PARTICIPANTS

There is a slight risk associated with vein punctures. We will make every effort to obtain the samples during a standard of care blood draw. If this is not possible, the risks associated with a blood draw include pain, dizziness, fainting, infection (rare), and redness. There is also a risk of loss of confidentiality, which will be minimized by efforts to secure the data.

POTENTIAL BENEFITS TO PARTICIPANTS

There will be no direct benefit to patient. We hope that the existence of this data will facilitate fundamental and significant research in advanced heart failure, ultimately benefitting patients in the future.

STATISTICAL ANALYSIS, DATA MANAGEMENT, AND CONFIDENTIALITY

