Statistical analysis will be performed using SPSS Statistics 22 (SPSS Inc, Chicago, IL, USA). Variables with 2-tailed p value <0.05 will be considered significant. Clinical parameters and outcomes including rates of GI bleeding, angiogenesis-related biomarkers, inflammatory markers, and microbiome data will be compared between the O3FA and control groups, both among the primary and secondary prevention arms using unpaired t-test or Mann-Whitney U test as appropriate. A necessary patient number for each group is calculated as 26 (total 104) by power analysis with 0.05 of α , 0.8 of effect size, 0.8 of $1-\beta$.

A master list maintaining patient names and code numbers will be stored in locked files. A password-protected computer located in the heart failure main office will contain a database for data collected in this study. Case report forms (CRF's) will be generated and filled out for each subject enrolled in this study.

There is a risk of loss of confidentiality. If a patient agrees to participate, and signs an informed consent, a signed copy of the consent will be given to them, a copy placed in their record and then the data will be abstracted into an electronic database. The database will be within the Department of Medicine, Section of Cardiology. The data will be password protected and covered by all of the firewalls and security features of the Department of Medicine.

The investigators seek to minimize these risks by labeling the study related data and specimens with a study code. This study code will be linked with the patient's data. Only the investigators

and their designated staff will have access to the databases and the link between study code numbers and patient identifying information.

Data and samples may be utilized by faculties who have the proper IRB approval to do so, and whose study objective meets with the overall objective of this research.

We may share coded data and/or samples outside of the institution in collaboration efforts. An IRB amendment will be submitted to the IRB for review if this happens. Additionally, if NIH funding is obtained for any proposed study, it is possible that the PI will be required to provide a copy of coded data to the NIH for public use. In either case, direct patient identifiers will never be shared.

ECONOMIC BURDEN TO PARTICIPANTS

There will be no economic burden to the participants.

CONSENT PROCESS

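### Withdrawing non-compliant O3FA patients and erasing their data removes randomised patients from one group only, and the resulting bias cannot be repaired afterwards

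*Combined protocol and SAP*

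**What the plan says.** The section on withdrawal of participants has two routes out of the trial, and both end in erasure.

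- **Withdrawal by the team:** "Participants can be withdrawn without consent if they are not compliant with taking O3FA daily". The next sentence reads: "They will be notified of withdrawal and all their data will be permanently erased". No level or duration of non-compliance is given, and the wording is permissive.
- **Withdrawal by the participant, in either group:** the supplement is returned "and the all of their data will be permanently erased".

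Other sections determine whom the first route can reach:

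- **Objectives, Aim 1a:** "Patients will be enrolled up to 3 months following CF-LVAD implantation and randomized to high-dose O3FA or none". Aim 1b uses the same contrast, so controls receive no O3FA.
- **Procedures involved:** the item "Study drug compliance check" appears at every visit from 1.5 months to 1 year, always under the heading for O3FA subjects. The trial is open-label, with 30 patients per group in each prevention arm.
- **Statistical analysis:** outcomes "will be compared between the O3FA and control groups, both among the primary and secondary prevention arms", by t-test or Mann-Whitney test. No analysis population and no missing-data rule are given.
- **Blood collection:** medical records will be used "for up to 2 years post-randomization to collect outcomes and adverse events".

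**The concern.** Randomisation protects the comparison only if patients are analysed in the groups to which they were allocated. Here the team may remove a patient after randomisation, for a reason that can arise in one group only, while knowing the allocation and possibly the patient's course so far. The control group keeps its would-be non-adherers; the O3FA group may lose its actual ones.

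If non-adherers tend to do worse, the retained O3FA group looks better than it should. If they tend to do better, it looks worse. The documents do not show which applies.

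Most gaps in an analysis plan can be closed later by going back to the full randomised set. Erasure rules that out for the trial dataset. It also removes bleeds and adverse events already recorded in treated patients. They stay in the medical record, and the planned regular review of events may have seen them first, but they would be missing from the reported comparison.

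**Working it through.** **The plan's own figure.** For a two-sample t-test with two-sided alpha 0.05, effect size 0.8 and power 0.80, n = 25.52, rounded up to 26 per group. Four groups give 4 × 26 = 104, which matches the plan. Enrolling 30 per group allows for a loss of 1 − 26/30 = 13.3%. That margin covers numbers, not selection.

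**Inputs.** From the plan: 30 vs 30 in each prevention arm and a two-sided 0.05 level. Assumed, because the documents give neither: the fraction *f* of the O3FA group erased, and the link between adherence and outcome. Every bias calculation below assumes no true O3FA effect.

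**Bleeding.** Let adherers have risk *p* and non-adherers *kp*, with the same mix in both groups. Controls then have average risk p(1 − f + fk). The O3FA group, with its non-adherers erased, has risk *p*. So

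apparent RR = 1 / (1 − f + fk).

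The risk level cancels.

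| Erased | k = 0.5 | k = 1 | k = 2 | k = 3 |
|---|---|---|---|---|
| 5% | 1.03 | 1.00 | 0.95 | 0.91 |
| 10% | 1.05 | 1.00 | 0.91 | 0.83 |
| 20% | 1.11 | 1.00 | 0.83 | 0.71 |
| 30% | 1.18 | 1.00 | 0.77 | 0.63 |

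As an illustration, the retrospective cohort in the Background section had 79% of controls event-free at one year, a risk of 21%. With f = 0.2 and k = 2, the adherers' risk is 0.21/(0.8 + 0.4) = 17.5%. The apparent comparison is 17.5% vs 21%, although the supplement does nothing. At 21%, only about 0.21 × 30 = 6.3 bleeders are expected among 30 controls, so one or two erased bleeders matter.

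**Markers.** I took 200,000 simulated null trials per case, 30 vs 30, with the outcome correlated with a latent adherence variable. The least adherent O3FA patients were deleted and an unpaired t-test was run at 0.05.

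| O3FA patients erased | Correlation 0 | Correlation 0.3 | Correlation 0.5 |
|---|---|---|---|
| 3 of 30 | bias 0; 5.0% | 0.055 SD; 5.6% | 0.092 SD; 6.7% |
| 6 of 30 | bias 0; 5.0% | 0.102 SD; 6.7% | 0.169 SD; 9.9% |
| 9 of 30 | bias 0; 5.0% | 0.145 SD; 8.1% | 0.241 SD; 14.0% |

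Percentages are two-sided type I error. A correlation of opposite sign gives the same sizes in the other direction. With 1 of 30 erased, the bias is about 0.02 to 0.04 SD and the type I error about 5.1% to 5.4% over the same correlations.

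**Power.** Noncentral t, effect size 0.8, controls held at 30:

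| O3FA patients left | 30 | 27 | 24 | 23 | 22 |
|---|---|---|---|---|---|
| Power | 86.1% | 84.2% | 81.8% | 80.8% | 79.8% |

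Power falls below 80% only when 8 or more are erased, so loss of power is secondary to bias.

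**The case against.** The strongest reply is that the rule may hardly ever be used. It is optional, patients with problems likely to impair compliance are excluded at entry, and participants are seen every 1.5 months. With 0% to 5% erased, the distortion is nil or small. The primary endpoint is a change in markers, and with 3 erased the type I error is still only 5.6% to 6.7%. Without a threshold, removals might also follow adherence less closely than the simulation assumes. All of this stands as a statement about size. It does not help the rule: how often it is used is left to an unblinded team, and nothing caps it.

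It can also be said that exclusions would be visible, because the groups are planned at 30 each and the master list or randomisation record may survive. That is fair. A shortfall would show that patients had been removed, but it would neither measure the bias nor correct it.

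The follow-up statement sets an upper limit of two years, so erasure can be read as an exception and not a formal contradiction. That reading is possible, but erasing recorded outcomes still sits badly with a stated intention to collect them, and the two sections should be reconciled.

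Finally, erasure after voluntary withdrawal applies to both groups and may reflect a promise to participants. This stands: it is a separate problem of lost outcomes, and what can be kept depends on consent. It does not excuse erasure when the team withdraws someone without that person's agreement.

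**Conclusion.** The concern holds and must be fixed. Followed as written, the plan allows discretionary, one-sided deletion of randomised patients in an open-label trial, with no analysis set to limit it. That only O3FA patients can be reached is inferred from the design, not stated, but a control group given no O3FA leaves no other workable reading.

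The size is uncertain. It is zero if the rule is never used or if adherence is unrelated to outcome. Over 10% to 30% erased and a risk in non-adherers of 0.5 to 3 times that in adherers, the apparent bleeding risk ratio under no effect runs from 1.18 to 0.63. For markers, the type I error runs from 5.0% with no correlation to 14.0% with 9 erased and a correlation of 0.5. These ranges are assumptions, not estimates from the documents. The severity comes from the fact that the loss is irreversible in the trial dataset.

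**What to change.** 1. In the section on withdrawal of participants, remove both erasure statements. Keep all data collected up to withdrawal, as consent allows.
2. For participants who miss or stop O3FA, continue the samples, chart follow-up and adverse-event recording already planned, in the group to which they were randomised, unless they withdraw consent. Whether the supplement itself is stopped is a clinical matter outside this point.
3. Reconcile this section with the two-year follow-up statement.
4. In the statistical section, state that the main analysis includes all randomised patients as randomised, and say how missing outcomes are handled.
5. Record the result of each compliance check and use it only in a secondary per-protocol analysis. That analysis selects within the O3FA group alone and carries the same asymmetry, so it should be labelled accordingly.

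The cost is a protocol amendment with matching consent wording. No extra patients or procedures are needed, and 30 vs 30 keeps power at 86.1% for effect size 0.8. The price is that non-adherence may dilute the estimated effect. For participants already enrolled, what may be kept after voluntary withdrawal has to be checked against the form they signed, which is not among the documents.

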The data presented thus far shows a possible link between O3FA, GI bleeding, and abnormal angiogenesis, and may be related to the microbiome in CF-LVAD patients. This prospective randomized study aims to evaluate the effect of supplemental O3FA on the frequency of GI bleeding in patients implanted with CF-LVAD both as primary and secondary prevention.

Additionally, we will investigate the effect of O3FA on angiogenesis parameters (Ang-1, Ang-2, VEGF, TNF- α) and the microbiome.

STUDY ENDPOINTS

The primary endpoint will be a change in angiogenesis markers resulting in dysregulated angiogenesis, as described above. Secondary endpoints include rate of GIB and improvement in inflammatory markers.

STUDY INTERVENTION

The study intervention being evaluated is high-dose O3FA (4,000 mg), which is an over-the-counter supplement. Heart failure patients are routinely instructed to take an O3FA supplement for heart health. The research team will fund the supplement, which will be stored in the heart failure office. Once a patient is enrolled, a total of 1 year of supplement will be given to the patient for consumption at home.

PROCEDURES INVOLVED

We will perform an open-label, prospective, randomized control study in which 120 CF-LVAD patients are enrolled. We plan to have 2 separate arms: primary prevention and secondary prevention (60 in each arm). In the primary prevention arm, 60 patients who have received CF-LVAD implantation and have not experienced any episodes of GI bleeding will be assigned to an O3FA group or a control group, with 30 patients in each group. In the secondary prevention arm, 60 LVAD patients who have experienced at least 1 episode of GI bleeding after CF-LVAD implantation will be assigned to an O3FA group or a control group, with 30 patients in each group. Randomization will be performed using computer software, and initiation of therapy will start within 24 hours of randomization. O3FA will be given at a dose of 4,000 mg orally per day, and all patients will receive guideline-directed medical therapy during the study period.

The following study procedures will be performed:

Baseline

Subject to sign consent
Verify inclusion/exclusion criteria
Record medical history and medications
Collect stool sample
Collect blood sample
Randomization
For O3FA subjects:
-Provide O3FA supplement
-Subjects will be instructed to take 4 pills a day

1.5 months post-randomization

Record medical history and medications
Record adverse events

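### The primary endpoint fixes no marker, visit, change measure or success rule, so a positive primary result need not carry the stated 5% error level

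*Combined protocol and SAP*

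**What the plan says.** - **Study Endpoints.** "The primary endpoint will be a change in angiogenesis markers resulting in dysregulated angiogenesis, as described above". The next sentence reads "Secondary endpoints include rate of GIB and improvement in inflammatory markers".
- **Background, last paragraph**, just before the endpoints: "Additionally, we will investigate the effect of O3FA on angiogenesis parameters (Ang-1, Ang-2, VEGF" and TNF-α). Earlier Background text gives the rationale, including an abnormal Ang-1 to Ang-2 balance and a role for TNF-α. It does not define an endpoint.
- **Objectives, Aims 1a and 1b.** "Markers of angiogenesis and inflammation will be assessed prior to and following initiation of high-dose O3FA therapy".
- **Procedures Involved, visit schedule.** Blood is drawn at baseline and at three later visits: "3 months post-randomization", then 6 months and 1 year.
- **Blood Collection.** One list has 13 angiogenesis factors, including Ang-2 and VEGF-A, -C and -D. A second has six inflammatory markers, including TNF-α. sCD40L is on both lists; Ang-1 is on neither.
- **Statistical Analysis.** Biomarkers are compared between O3FA and control "both among the primary and secondary prevention arms using unpaired t-test or Mann-Whitney U test as appropriate". The threshold is "Variables with 2-tailed p value <0.05 will be considered significant". On sample size: "A necessary patient number for each group is calculated as 26 (total 104) by power analysis", with α 0.05, effect size 0.8 and power 0.8. No multiplicity control appears in this section or elsewhere.

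**The concern.** A primary endpoint should let two analysts who have never spoken run the same test. Here they could differ on which marker or markers count, which of three visits is used, whether the follow-up value, the change or a baseline-adjusted value is compared, and how many markers must move. In an open-label trial with no other safeguard in the text, these choices can be made after the data are seen.

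Two things are at stake. First, if one significant marker is enough, a positive primary result does not carry the 5% error level that the statistics section implies. Second, the sample size was set for a single test that the protocol never identifies.

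Two lesser inconsistencies add to the ambiguity. The protocol says that Ang-1 will be investigated but lists no assay for it. TNF-α is an angiogenesis parameter in Background but an inflammatory marker under Blood Collection, and sCD40L is listed as both. Improvement in inflammatory markers is a secondary endpoint, so the same analyte could be reported as primary or secondary.

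**Working it through.** **1. The plan's own figure.** Inputs from the statistics section: two-sided α 0.05, standardised effect d = 0.8, power 0.80. The normal approximation gives n = 2(1.96 + 0.8416)²/0.8² = 24.5, so 25 per group. The noncentral t calculation gives 25.5, so 26 per group, and 4 × 26 = 104. The stated figure reproduces. Power is 0.807 with 26 per group and 0.861 with the planned 30. This is one test, at the full 0.05, in each arm.

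**2. How many markers could count.** The reference back in the endpoint most naturally points to the parameters named in Background. Of those, the assayed ones are:
- Ang-2 and one VEGF: 2 tests
- Ang-2, one VEGF and TNF-α: 3
- Ang-2 and VEGF-A, -C, -D: 4
- the last set plus TNF-α: 5

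The broad reading takes the whole angiogenesis list: 13.

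**3. False-positive chance under an any-one-marker rule** (O3FA affects no marker, one visit, one arm, 30 per group). For independent markers it is 1 − 0.95^k; for example, 1 − 0.95² = 0.0975 and 1 − 0.95⁵ = 0.226. The protocol gives no correlations, so equal correlations of 0.5 and 0.9 are assumed and unpaired t-tests simulated:

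| Markers | Independent | Correlation 0.5 | Correlation 0.9 |
|---|---|---|---|
| 2 | 9.75% | 9.3% | 7.1% |
| 3 | 14.3% | 12.6% | 8.6% |
| 4 | 18.5% | 15.5% | 9.4% |
| 5 | 22.6% | 18.3% | 10.3% |
| 13 | 48.7% | 33.9% | 14.2% |

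Every entry exceeds 5%.

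**4. One marker, but visit or measure left open** (one arm). Taking the best of the three visits gives 14% to 8% for assumed between-visit correlation 0 to 0.9. Taking the best of follow-up value, change score and baseline-adjusted value gives 9% to 10% for assumed baseline correlation 0.3 to 0.7.

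**5. Rules that would protect the error rate.** At one fixed visit and measure, requiring all of three markers gives 0.01% to 2.4% (correlation 0 to 0.9), and one composite gives 5%. If the visit stays open, a single composite behaves like the single marker in step 4. The all-markers rule with the best of three visits gives 6.0% to 6.6% at marker correlation 0.9 (between-visit correlation 0.5 and 0), and about 2.5% at marker correlation 0.7. So the 5% limit is assured only when visit and measure are fixed too.

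**6. Power if several markers stay primary.** With Bonferroni control, d = 0.8 and 30 per group, power for a given marker falls from 0.861 to 0.785 (2 markers), 0.735 (3), 0.698 (4), 0.668 (5) and 0.538 (13).

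**7. Ang-1.** Background names it as a parameter to be investigated, and neither Blood Collection list contains it. The Ang-1/Ang-2 ratio therefore cannot be formed from the listed assays.

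**The case against.** The p<0.05 sentence is a per-comparison convention. It does not say that one significant marker makes the trial positive, and an all-markers rule or a composite may have been intended. This stands: the inflation is conditional. The missing definition is not, because no section states either rule, and neither is sure to hold 5% without a fixed visit and measure.

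Aims 1a and 1b concern different populations, so 0.05 in each is defensible. This also stands. The trial-wide 1 − 0.95² = 9.75% for one marker in two arms matters only if a single overall claim is made.

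The power loss can be called modest: 0.785 for two markers against a target of 0.80. Power for at least one marker is about 0.88 at correlation 0.7 if every marker has d = 0.8. That is fair, and power is not the main issue.

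A reader might infer three stronger things that the documents do not support:
- **That the trial's error rate is 49%.** That figure needs all 13 factors, independence and an any-one-marker rule, none of which the protocol states.
- **That the sample size is wrong.** It reproduces for one test per arm.
- **That the Ang-1/Ang-2 ratio can never be obtained.** Data and Specimen Banking keeps blood for later related research, so Ang-1 might be measured if suitable sample remains.

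**Conclusion.** The point holds and must be fixed before analysis. What is certain is that the primary endpoint is not defined well enough to be tested in only one way, and that nothing controls multiplicity.

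If any one marker suffices, the false-positive chance at one visit in one arm is about 7% to 10% with two markers and 10% to 23% with five; the broad 13-factor reading gives 14% to 49%. These ranges rest on assumed equal correlation from 0.9 down to 0. The direction is firm under that rule, but no single figure can be called the trial's error rate.

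The Ang-1 mismatch is real but separate and of lesser weight, and it does not affect the false-positive rate. The double classification of TNF-α and sCD40L is a minor reconciliation item.

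**What to change.** Before analysis:

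1. Name one primary marker that is on the assay list (for example Ang-2), one visit and one baseline-referenced measure. Change from baseline fits the tests already stated. A baseline-adjusted follow-up value would need its test added to the statistics section.
2. Test it at two-sided 0.05 in each arm and declare Aims 1a and 1b separate questions. For one overall claim, use 0.025 per arm.
3. Make all other markers and visits secondary or exploratory, with Holm or false-discovery-rate adjustment.
4. If an all-markers or composite rule is intended instead, state it with its markers, visit and measure.
5. Reconcile Background with Blood Collection on Ang-1: add it if the platform can measure it (stored blood may allow this), or remove it from the parameters to be investigated. Assign TNF-α and sCD40L to one endpoint family each.

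**Cost.** Items 1 to 3 are wording only. With separate questions the sample size is unchanged and power at d = 0.8 stays 0.86 with 30 per group. Splitting α lowers it to 0.785 (from 0.807 to 0.716 with 26). An all-markers rule with three markers, each at d = 0.8, would have power of 0.63 (independent) to 0.80 (correlation 0.9) with 30 per group. The main downside is that fewer markers can be called significant. Adding Ang-1 depends on an assay capability that the protocol does not show; removing it is wording only.
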